# 2. Trial objective and endpoint

# 2.1. Objectives

The purpose of this randomized, double-blind, placebo-controlled study will be to evaluate whether the daily intake of Keranat™ for 24 weeks can promote the gloss and elasticity of hairs, improve their density and strength, and reduce hair loss.

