#### 2.1.1. Primary Objective

- To evaluate the change in hair elasticity between the Keranat™ and placebo group at baseline and 24 weeks, as measured by Expert 7601Tension Testing System.
- To evaluate the change in hair gloss between the Keranat™ and placebo group at baseline and 24 weeks, as measured by Skin-Glossy meter GL200.

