#### 2.2. Trial Endpoints

### 2.2.1. Primary Endpoints

- The change of hair elasticity: Change of the week 24 from baseline
- The change of hair gloss: Change of the week 24 from baseline

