#### 8.2. Definition of trial populations included in the analysis

- The efficacy analyses will be performed on the PPS(Per protocol set), defined as all randomized subjects by their assigned treatment arms.
- The PPS(Per protocol set) will be defined as subjects receiving randomized treatment, who meets entry criteria, have not permanently discontinued treatment administration and had no major protocol deviation
- Additionally, efficacy analyses will be performed on a FAS(Full Analysis Set).
- All safety analyses will be performed on the Safety Set, defined as all patients who
  received at least one dose of the treatment.
- Tests of normality will be performed to evaluate the data distribution. Test group of continuous variables will be compared to the placebo group using Independent T-

test, analysis of covariance, and the Wilcoxon rank-sum test. Comparison between groups according to changes in time will be analyzed using Paired T-test. Categorical data will be analyzed using the chi-square test or Fisher's exact test. A two-sided test will be considered significant when the p value <0.05.

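### Hair elasticity and hair gloss are both primary at an unadjusted p < 0.05 with no success rule; if either one counts as success, the false-positive chance is about 7% to 10%, not 5%

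*Combined protocol and SAP*

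**What the plan says.** Section 2.1.1 gives two primary objectives, one opening "To evaluate the change in hair elasticity between the" and the other "To evaluate the change in hair gloss between the". Section 2.2.1 lists the matching endpoints, "The change of hair elasticity: Change of the week 24 from baseline" and "The change of hair gloss: Change of the week 24 from baseline", without ranking them.

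Section 8.2 sets one threshold for every test: "A two-sided test will be considered significant when the p value <0.05". For continuous variables it names the independent t-test, "analysis of covariance, and the Wilcoxon rank-sum test". The same bullet opens by saying that normality will be tested, but it does not say what follows from the result.

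On analysis sets, Section 8.2 puts efficacy on the PPS first and then says "Additionally, efficacy analyses will be performed on a FAS(Full Analysis Set".

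Section 8 says that a detailed SAP will be written after the protocol is final and completed before unblinding, following the main features in the protocol. Section 8.1 uses a single undivided alpha of 0.05.

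**The concern.** With two primary endpoints, a 5% threshold on each test does not by itself fix the error rate of the primary conclusion. That rate depends on what counts as success, and the plan does not say. If either endpoint is enough, two chances at 5% give a combined rate above 5%. If both are needed, the rate is controlled and the price is power.

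The practical risk is a split result, for example gloss significant and elasticity not. The documents give no reading for it, so the rule could be chosen after the results are known. The open choice among three tests adds to this, because each primary endpoint can produce more than one p-value.

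**Working it through.** **1. The plan's own figure.** Section 8.1 assumes changes of 16.9 (SD 15.6) and 4.5 (SD 14.9).
- Pooled SD = √((15.6² + 14.9²)/2) = √232.685 = 15.254; standardised effect = 12.4/15.254 = 0.813.
- A two-sided two-sample t-test (noncentral t) at alpha 0.05 and 95% power needs 41 per group, as stated.
- So the full 0.05 was used and nothing was set aside for a second primary endpoint. The outcome sized is hair count, which is secondary, so the calculation does not show which primary endpoint leads.

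**2. One test per endpoint, either counts as success.** The inputs are two endpoints (2.2.1), a two-sided 0.05 for each (8.2), and no true effect on either. The correlation r between the two test statistics is not in the documents, so a range is assumed.
- At r = 0: 1 − (1 − 0.05)² = 1 − 0.9025 = 9.75%.
- For r > 0: 1 − P(|Z₁| < 1.96 and |Z₂| < 1.96), with Z₁ and Z₂ bivariate normal.
- Upper bound for any dependence: 0.05 + 0.05 = 10%.

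| Assumed r | Either p < 0.05 | Either p < 0.025 (Holm first step) | Both p < 0.05, both favouring Keranat |
|---|---|---|---|
| 0 | 9.75% | 4.94% | 0.06% |
| 0.5 | 9.07% | 4.65% | 0.46% |
| 0.7 | 8.35% | 4.30% | 0.83% |
| 0.9 | 7.04% | 3.62% | 1.48% |

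The second column falls to 5% only at perfect correlation. Counting only false positives in Keranat's favour, the either-endpoint rate at r = 0 is 1 − 0.975² = 4.94%, against a nominal 2.5%.

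**3. Both required.** A false joint claim needs a false positive on at least one endpoint that has no effect. Even if the other endpoint truly works, the rate cannot exceed that one test's 5% (2.5% in Keranat's favour).

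**4. More than one test per endpoint.** These figures are simulated and rest on assumptions that Section 8.2 does not state: t-test and Wilcoxon on change scores, ANCOVA with baseline as covariate, normal data, 41 per group, baseline to week-24 correlation 0.5, r = 0, and no true effect.

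| Reading of Section 8.2 | At least one primary endpoint p < 0.05 |
|---|---|
| Normality test (Shapiro-Wilk at 0.05 in each group, assumed) decides t-test or Wilcoxon | about 10% |
| As above, with ANCOVA also a free choice when normality holds | about 13% to 14% |
| Smallest of all three p-values (worst case) | about 15% to 16% |

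For the worst case, the single-endpoint rate is 8.1%, and 1 − (1 − 0.081)² = 15.5%. Varying the baseline to week-24 correlation from 0.3 to 0.7 moves the worst case from 16.2% to 14.5%. Choice between analysis sets is not included in any row.

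**The case against.** Several points on the other side have force.

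- **The SAP is still to come.** A success rule is a normal SAP item, and Section 8 commits to finalising that SAP before unblinding. This stands as a reason not to rate the matter higher than a should-fix. It does not close the gap, because the SAP is to implement the protocol's main features and the protocol contains no such rule.
- **Significance of a test is not success of the trial.** This is correct. A reader might infer that the plan, as written, has an inflated error rate. The documents do not support that: Section 8.2 says when a test is significant, not when the trial is positive. The 5% in Section 8.1 belongs to a hair-count calculation and is not a stated familywise commitment. The inflation is conditional on an either-endpoint reading.
- **A joint rule might be implied.** Section 2.1 says the product "can promote the gloss and elasticity of hairs", but that general aim continues to density, strength and hair loss, so it is not a both-required rule. The single primary comparison in Section 8.1 is between arms, not endpoints.
- **Normality testing probably selects the test.** This is the natural reading, and under it the rate stays near 10%. A reader might take 15% to 16% as the plan's error rate, but no passage permits picking the smallest of three p-values. What remains is that the link to normality is not written and ANCOVA has no stated role.
- **The analysis sets are ordered.** The word opening the FAS sentence indicates that PPS leads and FAS supplements it. A reader might infer a free choice between the two, and the text does not support that.

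**Conclusion.** The concern holds in conditional form. With two unranked primary endpoints, an unadjusted 0.05 on each and no success rule, an either-endpoint claim carries a false-positive chance of 7.0% to 9.75% for assumed correlations of 0.9 down to 0, bounded by 10%. A both-required claim stays at or below 5%. These figures assume one test per endpoint, jointly normal statistics and no true effect on either; the 10% bound needs no normality. The unspecified choice of test is a secondary issue, and its size depends on the reading and on the assumptions listed with the simulation. This should be fixed before unblinding. It is not evidence that the trial will make a false claim.

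**What to change.** Add two statements to Section 8.2 before unblinding.

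1. **One primary test in one set.** For each primary endpoint, name a single decisive test, for example ANCOVA of the week-24 change with the baseline value as covariate, in one named primary analysis set. The other tests and the other set become sensitivity analyses that do not decide success. The two PPS definitions must be reconciled first: one bullet describes all randomised subjects by arm, the next restricts the set to eligible, treated subjects without permanent discontinuation or major deviation.
2. **One success rule.** Either (a) for a claim on either endpoint, use Holm at familywise two-sided 0.05: the smaller p-value is compared with 0.025 and, only if that is significant, the other with 0.05, with success claimed only for a difference favouring Keranat. Or (b) for a combined claim, the trial is positive only if both endpoints have p < 0.05 favouring Keranat.

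Statement 1 is needed for option (a) to work. In the worst case of the smallest of three p-values, the Holm first step at 0.025 still gives about 8.2% at r = 0, against 4.9% with one named test.

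**Cost.** Trial conduct does not change, but some power is lost. The documents give no effect size or SD for elasticity or gloss, so the following is illustrative only. It assumes independent endpoints with equal marginal power of 80%, 90% or 95% at 0.05.
- Either endpoint at 0.05: 1 − 0.20², 1 − 0.10², 1 − 0.05² = 96%, 99%, 99.8%.
- Holm, at least one endpoint: by normal approximation, marginal power at 0.025 is 71.2%, 84.1%, 91.4%, giving 1 − 0.288², 1 − 0.159², 1 − 0.086² = 91.7%, 97.5%, 99.3%.
- Both required: 0.80², 0.90², 0.95² = 64%, 81%, 90%.

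Holm therefore costs little, and requiring both costs considerably more. The sponsor should choose according to the claim it wants to make.

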# 9. Confidentiality

Records confirming the subject's identity will be kept confidential. Monitoring staff and officers involved in the study may access subject records for the purpose of monitoring, reviewing, or managing the progress of the study, but such information will also be kept confidential. All documents related to the study, such as case records, will be recorded and distinguished using a subject identification code, not subject name. The collected information will be kept in the document storage room of the research institute for 3 years after the end of the study and will be discarded after 3 years according to the standards and procedures prescribed by the Personal Information Protection Act. During or after the study, research data, including medical records, may be reviewed to verify the conduct of the study and the reliability of the data, but this access is limited to the extent to which confidentiality of each subject's identity is protected.
